### 4.4 Selection of Patients

### 4.4.1 Inclusion Criteria

Each patient must meet all of the following inclusion criteria to be enrolled in the study:

Title: Absorption and Safety with Sustained Use of Relizorb™ Evaluation (Assure) Study in Patients With Cystic Fibrosis Receiving Enteral Feeding

1. Male or female patients 4 years of age or older

- Confirmed diagnosis of CF defined as two clinical features consistent with CF and have either:
  - a. Genotype with two identifiable mutations consistent with CF, determined using diagnostic devices that have been cleared by the US FDA (the FDA clearance requirement does not apply if the test was performed prior to 2005, the year the US FDA first started evaluating genetic tests for CF), or
  - b. Sweat chloride >60 mEq/L by quantitative pilocarpine iontophoresis
- Documented history of exocrine pancreatic insufficiency due to CF (e.g., historical fecal elastase test, genotype consistent with exocrine pancreatic insufficiency, etc.)
- Enteral formula user a minimum of four to five times per week, using PERT, consuming an unrestricted fat diet, and willing to use Peptamen 1.5 and Impact Peptide 1.5
- 5. Clinically stable with no significant changes in health status within 14 days of Day -14
- 6. Written informed consent obtained from patient, or, if the patient is a minor, from the patient's legal representative with assent from the minor when applicable.

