6.3.1 Weight and BMI Derived Variables

Up to 4 weight, height, and body mass index (BMI), (and BMI percentile for subjects of age ≤18 years) recordings will be obtained from the medical record at approximately 3 month intervals over the previous 12 months prior to Visit 1 on Day -14. Weight and BMI will be collected at Visit 1 (study entry; Day -14) and at study visits on Day 0 (Visit 2), Day 30 (Visit 3), Day 60 (Visit 4), and Day 90 (Visit 5).

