6.3.1.1 Weight Gain Velocity

Weight gain velocity (WGV) is defined as the rate of change in body weight per initial body weight per time period. The quantity will be expressed in units of g/kg/90 days.

The formula to calculate WGV between two dates Date1 and Date2 is:

90 x [weight (g) at Date2 – weight (g) at Date1] / [weight (kg) at Date1] / (Date2 – Date1 + 1)

The factor of 90 converts the rate from per day to per 90 days.

The WGV can be considered the slope as the change in weight (Δ w) divided by the change in days plus 1 (Δ t). This quantity is multiplied by 90 and then divided by the subject weight at interval start (kg) to express the results as 90-day changes for each kilogram of weight. For example, if a patient is 62.0 kg on January 1, 2016 and 63.5 kg on April 1, 2016, the slope is 1.5 kg/92 days = 1.5 kg/92 days = 1500 g/92 days = 16.3 grams per day. Equivalently, 90 days x 16.3 g/day equals 1467.4 g / 90 days. Expressed per kg body weight, the WGV equals 23.7 g/kg/90 days. Equivalently, as above, 90*(63500-62000)/62.0/92 = 23.7

WGV will be calculated from the date of Visit 2 to the date of Visit 5, or the last visit at which a weight is available.

The historical weight recordings will be used to calculate historical WGV. Any weights recorded more than 12 months before Study Entry and weights recorded before the date of tube placement indicated in medical history will be excluded. The selection of the appropriate medical indications and date imputations for this are described in Section 6.3 for the calculation of duration of enteral feeding. The historical WGV will be determined by first calculating the change in weight between each consecutive historical weight recorded before Study Entry and thus providing up to 3 values for change in weight. WGV will then be calculated from these weight changes as described above. The average of these values will be determined and identified as the average historical WGV.

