6.3.1.2 Weight and BMI Z-scores and Percentiles Derived Variables

Weight and BMI values from baseline (Visit 2 or Visit 1 if Visit 2 is missing) and Visit 3 to Visit 5 will be normalized to Z-scores based on age- and sex-specific data from the Centers for Disease Control and Prevention (CDC). A SAS program and dataset obtained from the CDC website will be used to calculate the values for healthy subjects aged 2-20 years, with age expressed in months with decimal. The CDC data is provided in half month intervals for age.

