8.3.2 Weight and BMI Z-scores

Age-specific z-scores for weight and BMI are obtained (via CDC standard tables) at each study visit and at quarterly intervals in the year prior to baseline. For weight and for BMI, the average historical distribution percentile (mean of historical values) and the z-scores (and distribution percentile) at 30, 60 and 90 days will be presented. The change in percentile of the distribution from historical average to 90 days will be tested by a one-sample t-test or Wilcoxon signed rank test. This analysis will be performed by age subgroup only.

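### Weights from before tube placement are dropped from historical weight gain velocity but not from the historical weight/BMI percentile average, so gain after placement can be tested as a RELiZORB effect

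*SAP*

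**What the plan says.** The SAP uses the prior year's medical-record measurements for two growth analyses.

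- **Shared source (SAP 6.3.1).** Up to four weight, height and BMI "recordings will be obtained from the medical record at approximately 3 month intervals over the previous 12 months prior to Visit 1". No condition on tube date is attached.
- **Weight gain velocity (SAP 6.3.1.1).** Weights more than 12 months before Study Entry are left out, and "weights recorded before the date of tube placement indicated in medical history will be excluded". The rule stands under the velocity heading and speaks of weights only.
- **Z-scores and percentiles, derivation (SAP 6.3.1.2).** "Weight and BMI values from baseline (Visit 2 or Visit 1 if Visit 2 is missing) and Visit 3 to Visit 5 will be normalized"; the reference is the CDC data. Historical values are not mentioned.
- **Z-scores and percentiles, analysis (SAP 8.3.2).** Z-scores are obtained "at each study visit and at quarterly intervals in the year prior to baseline". The reference is "the average historical distribution percentile (mean of historical values"; the parenthesis closes there, with no condition on tube date. Then: "The change in percentile of the distribution from historical average to 90 days will be tested by a one-sample t-test or Wilcoxon signed rank test". The test is done within age subgroups only.
- **Eligibility (Protocol 4.4.1).** The criterion is "Enteral formula user a minimum of four to five times per week". It fixes a weekly frequency, not a minimum time since placement.

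Protocol 7.8 gives the purpose of the historical comparison as evaluating what Relizorb does to weight and BMI.

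**The concern.** The growth question concerns the device in people who are already tube-fed. Protocol 2.3 says enteral nutrition is given to maintain or gain weight, so values from before placement are likely to be low for reasons unrelated to RELiZORB. The velocity rule shows that the SAP's authors saw this. A programmer who follows the text would apply the rule to velocity and not to the percentile average.

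For a subject with a recently placed tube, the tested null is then no change since a period that partly precedes tube feeding. A step up at placement lowers the historical mean and raises the Day 90 difference, in the device's favour, and there is no control arm to absorb it. SAP 8.3.2 names no other test of weight or BMI percentile. The two growth analyses would also rest on different histories from the same subjects. SAP 1 allows these results to go into study reports, submissions and manuscripts.

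**Working it through.** **The plan's own figures.** The plan states no power or error rate for this test. Its one power statement (SAP 3.2: 30 subjects, effect size 0.53, 80%) reproduces at 0.801 with a two-sided one-sample t-test, but it concerns the primary endpoint and has no bearing here.

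**Inputs from the documents.** Four quarterly historical values at most (SAP 6.3.1); a one-sample test of Day 90 minus the historical mean, by age subgroup (SAP 8.3.2); two-sided 0.05 with nominal p-values (SAP 6.1).

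**Inputs assumed, because the documents give none.**
- Share *f* of subjects with a tube placed in the prior 12 months.
- Placement date uniform over those 12 months; recordings at -12, -9, -6 and -3 months.
- A 0.5 z step gain at placement, flat otherwise, and no device effect.
- z distributed N(-0.5, SD 0.8); within-subject SD 0.15 z.
- Subgroups of 12 and 18.

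**Mean false gain.** Bias = *f* × (*m*/4) × *G*, where *m* is the number of pre-tube recordings and *G* the gain in percentile points.
- Expected *m* = 1 + 0.75 + 0.50 + 0.25 = 2.5.
- The mean percentile for z centred at μ is Φ(μ/√(1 + 0.8² + 0.15²)) = Φ(μ/1.289). That is 34.9 at μ = -0.5 and 21.9 at μ = -1.0, so *G* = 13.0.
- Bias = *f* × (2.5/4) × 13.0 = 8.1 × *f* percentile points.

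**Rejection with no device effect** (t-test on percentile change, 20,000 simulated trials per cell):

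| Share *f* | Mean false gain (points) | Rejects, n=12 | Rejects, n=18 |
|---|---|---|---|
| 5% | 0.4 | 4.8% | 5.4% |
| 10% | 0.8 | 5.7% | 7.3% |
| 20% | 1.6 | 9.4% | 14.3% |
| 30% | 2.4 | 16.1% | 26.3% |
| 50% | 4.1 | 38.6% | 59.7% |

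At 10% and n=12, about 80% of the rejections favour the device; from 20% upward nearly all do. At a 30% share, a gain of 0.3 z gives 11.0% (n=12) and 17.3% (n=18), and 0.8 z gives 19.4% and 34.4%.

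**A second, simpler model.** With half the recordings pre-tube, *G* of 10 to 20 points, SD of change 10 to 15 points and *f* from 10% to 50%, the bias runs from 0.1 × 0.5 × 10 = 0.5 to 0.5 × 0.5 × 20 = 5.0 points. In a subgroup of 10, the chance of a significant result in the device's favour is about 3% to 22%, against a nominal 2.5%.

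**With pre-tube values excluded.**
- Step gain: the *m*/4 term vanishes and rejection is 4.6-4.9%.
- The same 0.5 z spread evenly over 6 or 12 months after placement, at a 30% share: rejection after the exclusion is still about 10% and 12% (n=12), and about 15% and 18-19% (n=18). The mean false gain falls only from about 3.0 to 1.7 points (6 months) or from 2.5 to 2.0 points (12 months).

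**The case against.** Five things can be said on the other side.

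1. **The size is assumed throughout.** The share of recent placements may be zero, and then so is the bias. At 5% no inflation is visible, and at 10% it is slight. The rates near 40% and 60% need half of a subgroup to be recently placed, which nothing in the documents suggests. Subgroup sizes are not given either, and the CDC program in SAP 6.3.1.2 covers ages 2 to 20 only. This stands, and it limits the claim to a bias that can occur.
2. **The analysis is exploratory** (SAP 2.2.2 and 8.3), with nominal p-values. This stands: no primary or secondary conclusion is touched.
3. **Readers have other evidence.** Years of tube feeding before entry are tabulated and listed (SAP 7.3), baseline values are also normalized (SAP 6.3.1.2), and Protocol 7.8 plans an analysis of weight change from Day 0. These help a careful reader, but they do not alter the planned test.
4. **The velocity rule may have been meant for all historical values.** That is possible. But it sits under one derived variable, speaks only of weights, and is not referred to in 6.3.1.2 or 8.3.2.
5. **The date is a proxy.** The SAP uses gastrostomy placement, whereas eligibility is about formula use, so a weight before that date need not precede enteral feeding. This stands, and it applies equally to the velocity rule that the SAP already accepts.

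A reader might also infer that extending the exclusion brings the test back to 5%. That holds only if the whole gain is complete soon after placement. With gradual gain, most of the false gain remains.

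**Conclusion.** The inconsistency is in the text, and its direction is clear. Pre-tube weights are excluded from one historical growth reference and not from the other, and eligibility allows subjects for whom this matters. Weight gained after placement can therefore be tested as a RELiZORB effect.

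Under the stated assumptions, two-sided rejection with no device effect is about 6-7% at a 10% share of recent placements, 9-14% at 20% and 16-26% at 30%. It is nominal if there are none. The documents do not support the inference that the growth result will be false, or that the bias is large in this trial, because they do not give the share. The matter is confined to an exploratory subgroup analysis, but it is worth correcting because the rule and the date already exist.

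Pre-tube values are also only part of the weakness. A historical mean in a single-arm study carries any growth trend already under way, whatever is done about tube dates.

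**What to change.** - Move the exclusion in SAP 6.3.1.1 (values more than 12 months before Study Entry, or before tube placement) up to SAP 6.3.1, so that it covers every historical weight and BMI value.
- In 6.3.1.2, state that historical values are normalized in the same way as the study visits.
- In 8.3.2, state that the historical average uses post-placement values only, and that subjects with none are left out of the historical comparison.
- Show the change from Day 0 to Day 90 alongside, and say in the report that any trend already under way remains in this single-arm contrast.

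The cost is small. The placement date is already derived (SAP 6.3), and no new data are needed. Recently placed subjects will have fewer historical values, and a few may drop out. Under the uniform-date assumption, a quarter of them (tube placed in the last 3 of 12 months) have no post-placement value: at a 30% share and n=12, that is 12 × 0.30 × 0.25 = 0.9 of a subject.

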9. SAFETY AND TOLERABILITY ANALYSIS

The analysis of safety assessments in this study will include the following categories of safety and tolerability data collected for each subject:

- Adverse Events (AEs)
 - Serious Adverse Events
 - Unanticipated adverse device effect (UADEs)
 - UADEs leading to discontinuation of enteral feeding
 - Any deaths
- 7 day gastrointestinal symptom diary
- Clinical laboratory investigations
- Vital signs
- Concomitant medications

Exposure to treatment

Safety data will be summarized descriptively on the safety population.

9.1 Adverse Events

All AEs will be coded using the Medical Dictionary for Regulatory Activities (MedDRA Version 18.0 or most recent version).

AEs will be summarized by MedDRA system organ class and preferred term. Separate columns will be included in the AE summary table for AEs starting under the treatment by Standard of Care, and starting during RELiZORB treatment.

For all AEs, the event will be summarized under the treatment (Standard of Care, RELiZORB) the event started in and in the total column. The AE is assigned to the standard of care or RELiZORB based on the start date of the adverse event.

- If the start date of the event is before the first administration of RELiZORB, the event will be summarized under Standard of Care.
- If the start date of the event is on or after the first administration of RELiZORB, the event will be summarized under RELiZORB.
- If the start and end date of the event are both missing, the event will be summarized under both SOC and RELiZORB.

In a general overview of AEs, events will be summarized by treatment for the following items:

- All AEs
- Serious Adverse Events (SAEs)
- AEs by relationship
- AEs leading to discontinuation of enteral feeding
- AEs by maximum severity
- UADEs
- UADEs by relationship
- UADEs leading to discontinuation of enteral feeding
- UADEs by maximum severity

Missing and partially missing AE start and/or stop dates will be imputed, for the purpose of statistical analysis, according to the specifications described in Section 6.2.

Summaries of incidence rates (frequencies and percentages) of individual AEs by MedDRA System Organ Class and preferred term will be prepared. UADEs and SAEs will not be included in summaries of AEs, but will be summarized separately. Each subject will be counted only once within each level of summary (system organ class and preferred term).

Adverse events that lead to discontinuation of enteral feeding will be summarized and listed separately.

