### 6.2 Adverse Events

An adverse experience (AE) is defined as any untoward medical occurrence in a subject, regardless of its causal relationship to the investigational device. An AE can therefore be any unfavorable and unintended sign (including abnormal laboratory

Title: Absorption and Safety with Sustained Use of Relizorb™ Evaluation (Assure) Study in Patients With Cystic Fibrosis Receiving Enteral Feeding

findings), symptom or disease experienced with use of the product, whether or not it is related to the product. This includes any newly occurring event or a previous condition that has increased in severity or frequency since the use of Relizorb.

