# 6.2.2 Anticipated Adverse Events in Subjects

Due to the GI complications inherent in CF patients, the identified risks are upper abdominal pain, bloating, constipation, diarrhea, flatulence, heartburn, indigestion, nausea, steatorrhea (fatty stool), vomiting, weight decrease and headache.

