6.2 Handling of Missing Data

Available subject data will be used in the statistical analysis. For the MMRM analysis, subjects who lack all post-baseline measures, the baseline efficacy outcome will be imputed for all post-baseline responses (i.e., no change from baseline).

To handle missing or partial AE and medication dates, the following rules will be applied.

For partial start dates:

- 1. If the year is unknown, then do not impute the date but assign a missing value
- 2. If the month is unknown, then:
 - a. If the year matches the year of the first RELiZORB administration date, then impute the month and day of the first RELiZORB administration date.
 - b. Otherwise, assign "January."
- 3. If the day is unknown, then:

a. If the month and year match the month and year of the first RELiZORB administration date, then impute the day of the first RELiZORB administration date.

b. Otherwise, assign "01."

For partial end dates:

- 1. If the year is unknown, then do not impute the date but assign a missing value.
- 2. If the month is unknown, then assign "December."
- 3. If the day is unknown, then assign the last day of the month.

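### SAP 9.1 assigns AEs to Standard of Care or RELiZORB by start date with no provision for worsening on the device, and SAP 6.2 can impute a start date later than the event's known end

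*SAP*

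**What the plan says.** SAP 9.1 has two AE columns, Standard of Care and RELiZORB, and states the principle for filling them: "The AE is assigned to the standard of care or RELiZORB based on the start date of the adverse event". Three rules put it into effect:

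- Onset earlier than first device use sends the event to Standard of Care.
- Onset on that day or later sends it to RELiZORB.
- The third rule covers events without dates: "If the start and end date of the event are both missing, the event will be summarized under both SOC and RELiZORB".

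The overview in the same section tabulates relationship, maximum severity and discontinuation of enteral feeding by these columns.

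Protocol 6.2 defines an AE and adds: "This includes any newly occurring event or a previous condition that has increased in severity or frequency since the use of Relizorb". It does not discuss table columns.

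SAP 6.2 deals with incomplete dates. When only the day of the start is unknown, and month and year match first device use, the instruction is: "then impute the day of the first RELiZORB administration date". When the month is unknown and the year matches, the month and day of first use are both taken. When the start year is unknown, the date stays missing. No step compares the result with the end date.

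**The concern.** These columns are the plan's only before-and-after presentation of AEs by severity and relationship. An event that began as mild before the device and became severe on it carries safety information about the device period. Under a start-date rule that information can sit entirely in the column for the period when the subject had not yet used the device. The table could then show a severe event rated as device-related under Standard of Care.

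Gastrointestinal events are the likely setting. Protocol 6.2.2 introduces its list of anticipated events with "Due to the GI complications inherent in CF patients", so fluctuating complaints are to be expected.

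The partial-date rule raises a different problem. It can assign to the device an event that is known to have ended before the device was used.

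**Working it through.** The plan gives no figure to reproduce. The check traces cases through the stated rules.

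**Inputs.** Pre-device time is 7 + 7 = 14 days, followed by 90 days on the device, 104 in all (Protocol 4.2). Planned enrolment is about 35 (Protocol 4.1); SAP 3.3 gives 30 to 40. First use is on Day 0 (Protocol 4.9.9).

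**Worsening, three cases**

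1. An AE starts as mild on Day -5 and becomes severe on Day 40, in one record. The start is before first use, so it goes to Standard of Care. If the record carries the later grade and relationship, these go there too. Nothing appears under RELiZORB.
2. The same course, but the site opens a second record at the worsening. That record starts on Day 40 and goes to RELiZORB. The rule works.
3. A complaint already present at entry, hence medical history (Protocol 4.9.4), worsens on Day 40. Under Protocol 6.2 the worsening is an AE arising since device use. Recorded with that onset, it goes to RELiZORB. The rule works.

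Only case 1 fails. Neither the protocol nor the SAP tells sites to record a worsening as a separate event.

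**Size in case 1.** If the subject has no other on-device event at the same level of summary, the RELiZORB column is short by:

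- 1/35 = 2.9 percentage points at n = 35
- 1/30 = 3.3 points at n = 30
- 1/40 = 2.5 points at n = 40

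The Standard of Care count itself is right, because the event did begin there. What is wrong in that column is the severity and relationship attached to it.

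**Partial dates (illustrative dates)**

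- First use is 20 May, the start is known only as May, and the end is 12 May.
- Month and year match, so the imputed start is 20 May.
- End minus start = 12 - 20 = -8 days.
- The imputed start is on the day of first use, so the event is counted under RELiZORB, although it ended before first use.

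Here the event changes columns. At n = 35 the RELiZORB column can gain 1/35 and the Standard of Care column lose 1/35, a shift of up to 2/35 = 5.7 points in the difference.

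**Missing start, known end.** An unknown start year leaves the start missing. The first two rules of SAP 9.1 need a start date and the third needs both dates missing. No rule applies.

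**The case against.** The strongest reply is that the two documents fit together. Protocol 6.2 says what counts as an AE, not which column it belongs in. If a worsening is treated as its own AE, its start date is on the device and SAP 9.1 places it correctly. This stands. A reader might infer that the SAP contradicts the protocol's definition, but the texts show only that the SAP omits a provision. A reader might also infer that the rule removes from the RELiZORB column any worsening of complaints that patients bring into the study. Case 3 shows that it need not.

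Sites also follow eCRF completion guidelines (Protocol 5.1), which are not among the documents and may require a new record at worsening. That is possible, and it limits how sure one can be that case 1 would arise. It does not supply the missing rule in the SAP.

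The symptom diary is a partial safeguard. SAP 9.2 summarizes incidence and symptom days for each diary week, so more frequent gastrointestinal symptoms in those weeks would be visible. SAP 10 removes diary severity and duration, so a complaint that becomes more severe on the same number of days would not.

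The AE columns are descriptive (SAP 9), carry no planned test, and cover about 14 against 90 days, so differences between them already need caution.

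On dates, imputing to first use is conservative for the device when timing is truly uncertain. That holds in general, but not when a known end date settles that the event preceded the device. An unknown start year should be rare in a 104-day study.

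**Conclusion.** The point holds as a gap in the SAP's rules. For an event with pre-device onset, on-device worsening and a single record, SAP 9.1 reports the on-device severity and relationship only under Standard of Care. The RELiZORB column is then short by up to 2.9 points per subject at n = 35 (2.5 to 3.3 points for 40 to 30 subjects). This assumes that the subject has no other qualifying event at that level and that the site does not open a second record. The documents give no basis for how many subjects this would affect, so no total is claimed.

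The 5.7-point shift belongs only to the date error, where an event leaves one column for the other. It should not be applied to worsening.

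The two defects run in opposite directions: the first favours the device and the second counts against it. The documents therefore do not support a claim of net bias either way. The missing end-date check and the unallocated case with missing start and known end follow directly from the SAP text and do not depend on how sites keep records.

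**What to change.** **SAP 9.1.** Keep an event with pre-device onset under Standard of Care, at its pre-device severity. Count it also under RELiZORB, with its on-device maximum severity and relationship, if it becomes more severe or more frequent on or after first administration. Identify the worsening from a separate AE record or from whatever dated severity data exist. Moving the event out of Standard of Care would be wrong, since it did occur there.

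**SAP 6.2.** Never impute a start later than the known end date. In the example the start would be no later than 12 May, and the event would fall under Standard of Care.

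**SAP 9.1, missing start with known end.** If the end is before first use, place the event under Standard of Care; otherwise under RELiZORB.

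**Cost.** A few sentences and slightly more programming, best settled before database lock. The RELiZORB column may look slightly less favourable. SAP 3.3 describes enrolment in the past tense, so a new instruction to sites may come too late for some records. Where no dated severity exists, the worsening cannot be recovered and the report should say so.

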9.1.1 Unanticipated Adverse Device Effects

UADEs will be summarized separately for all UADEs, UADEAEs by maximum intensity, UADEAEs by strongest relationship to study device. Each subject will be counted only once within each level of summary (system organ class and preferred term). If a subject experiences more than one AE in each level, the AE with the strongest relationship or the maximum severity, as appropriate, will be included in each summary for AE relationship and severity.

All UADES and UADEs leading to discontinuation of Enteral Feeding will be presented in a listing.

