9.1.2 Serious adverse events

Serious Adverse Events (SAEs) will be listed separately but not summarized.

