14.2.1.7	ITT	Changes over Time in Serum Protein Concentrations (Total Protein, Prealbumin, Albumin, and Transferrin)	16.2.5.6.1
14.2.1.8	ITT	Changes over Time in Urinary Leukotriene E4	16.2.5.7.1
14.2.1.9a	ITT	Changes over Time in Plasma Concentrations of Fat Soluble Vitamins (A, D, and E)	16.2.5.5.1
14.2.1.9b	ITT	Changes over Time in Plasma Concentrations of Fat Soluble Vitamins (A, D, and E) by Age Subgroup	16.2.5.5.1
14.2.1.10	ITT	Weight and Body Mass Index (BMI) Z-scores by Age Subgroup and Comparison to Historic Z-score	16.2.5.10.1
14.2.1.11	ITT	Changes over Time in Weight Gain Velocity (g/kg/90 days) Compared to Historical by Age Subgroup	16.2.5.9.1
14.3.1.1	Safety	Summary of Adverse Events	16.2.6.1, 16.2.6.2, 16.2.6.3, 16.2.6.5
14.3.1.2	Safety	Adverse Events by System Organ Class and Preferred Term	16.2.6.1
14.3.2.1	Safety	Unanticipated Adverse Device Effects by System Organ Class and Preferred Term	16.2.6.3
14.3.2.2	Safety	Unanticipated Adverse Device Effects by System Organ Class, Preferred Term, and Relationship	16.2.6.3
14.3.2.3	Safety	Unanticipated Adverse Device Effects by System Organ Class, Preferred Term, and Severity	16.2.6.3

Table Number	Population	Title	Listing Reference
14.3.3.1	Safety	Gastrointestinal Symptom Diary: Frequency and Incidence – Overall and by Symptom	16.2.7.1
14.3.4.1	Safety	Summary of Clinical Chemistry Measurements: Results and Change from Baseline	16.2.8.1
14.3.4.2	Safety	Summary of Hematology Measurements: Results and Change from Baseline	16.2.8.2
14.3.4.3	Safety	Summary of Numeric Urinalysis Measurements: Results and Change from Baseline	16.2.8.3
14.3.4.4	Safety	Summary of Blood Lipids: Results and Change from Baseline	16.2.8.4
14.3.5.1	Safety	Summary of Vital Sign Measurements: Results and Change from Baseline	16.2.9.1
14.3.6.1	Safety	Concomitant Medications	16.2.3.3

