16.2.5.7.2	Subjects Excluded	Urinary Leukotriene E ₄ (LTE4)	
	from Per Protocol		
16.2.5.8.1	ITT	Weight, Height, and Body Mass Index	
16.2.5.8.2	Subjects Excluded	Weight, Height, and Body Mass Index	
	from Per Protocol	and the Control of th	
16.2.5.9.1	ITT	Weight Gain Velocity	
16.2.5.9.2	Subjects Excluded	Weight Gain Velocity	
	from Per Protocol	,	
16.2.5.10.1	ITT	Weight and Body Mass Z-scores	
16.2.5.10.2	Subjects Excluded	Weight and Body Mass Z-scores	
	from Per Protocol		
16.2.6.1	All Enrolled Subjects	Adverse Events	
16.2.6.2	All Enrolled Subjects	Adverse Events Leading to Discontinuation of	
		Enteral Feeding	
16.2.6.3	All Enrolled Subjects	Unanticipated Adverse Device Effects	
16.2.6.4	All Enrolled Subjects	Unanticipated Adverse Device Effects Leading to	
	- T	Discontinuation of Enteral Feeding	
16.2.6.5	All Enrolled Subjects	Serious Adverse Events	
16.2.6.6	All Enrolled Subjects	Deaths	
16.2.7.1	All Enrolled Subjects	Gastrointestinal Symptom Diary	
16.2.8.1	All Enrolled Subjects	Clinical Laboratory Tests: Chemistry	
16.2.8.2	All Enrolled Subjects	Clinical Laboratory Tests: Hematology	
16.2.8.3	All Enrolled Subjects	Clinical Laboratory Tests: Urinalysis	
16.2.8.4	All Enrolled Subjects	Clinical Laboratory Tests: Blood Lipids	
16.2.9.1	All Enrolled Subjects	Vital Signs	
16.2.9.2	All Enrolled Subjects	Physical Examination	
16.2.10.1 All Enrolled Subjects		Telephone Contact Log	

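### The SAP takes serious adverse events out of the only AE table by term, promises a separate summary, then says they will not be summarised, so Table 14.3.1.2 can understate incidence.

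*SAP*

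**What the plan says.** SAP 9 lists SAEs and UADEs as sub-items of adverse events and says in general terms that "Safety data will be summarized descriptively on the safety population".

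SAP 9.1 does three things with SAEs. It gives them a line in the general overview by treatment. It describes incidence summaries by MedDRA system organ class (SOC) and preferred term (PT). In that same paragraph it says "UADEs and SAEs will not be included in summaries of AEs, but will be summarized separately".

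SAP 9.1.1 carries this out for UADEs: "UADEs will be summarized separately for all UADEs", and also by intensity and by relationship. SAP 9.1.2 says the opposite for SAEs: "Serious Adverse Events (SAEs) will be listed separately but not summarized".

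The output lists match this split. SAP 12.1 has one AE table by term, Table 14.3.1.2 ("Adverse Events by System Organ Class and Preferred Term"), and three UADE tables by term, starting with Table 14.3.2.1 ("Unanticipated Adverse Device Effects by System Organ Class and Preferred Term"). The only output in SAP 12.1 or 12.2 devoted to SAEs is Listing 16.2.6.5 ("Serious Adverse Events"). Overview Table 14.3.1.1 cites that listing among its sources.

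SAP 10, which records changes from the protocol's analysis, does not mention leaving SAEs out of the AE incidence table.

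**The concern.** Sections 9.1 and 9.1.2 give a programmer opposite instructions on whether SAEs are summarised. Beyond the wording, the exclusion in 9.1 takes SAEs out of the one table that shows which AEs occurred and how often, and nothing planned puts them back by term.

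AE frequency and severity is a safety endpoint in protocol 3.2, and protocol 7.7 assesses safety on the incidence, severity and type of AEs. The protocol's AE definition (6.2) does not exclude serious events. A reader would naturally take Table 14.3.1.2 as complete incidence by term. If followed as written, it would omit the most serious events unless they were also classed as UADEs.

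**Working it through.** The plan states no figure on this point, so there is none to reproduce. The check is a reconciliation of the text with the output lists, followed by simple arithmetic for scale.

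**Step 1: where each class of event appears (SAP 9.1, 9.1.1, 9.1.2, 12.1, 12.2).**

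| Class of event | Overview (14.3.1.1) | Table by SOC/PT | Listing |
|---|---|---|---|
| AE, neither SAE nor UADE | yes | 14.3.1.2 | 16.2.6.1 |
| UADE | yes | 14.3.2.1, 14.3.2.2, 14.3.2.3 | 16.2.6.3 |
| SAE that is not a UADE | yes | none | 16.2.6.5 |

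Of the five planned AE and UADE tables, one is the overview and four are by term: 1 for AEs, 3 for UADEs, 0 for SAEs.

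**Step 2: can an SAE fail to be a UADE?** Under the protocol's definitions it can.

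- Protocol 6.2 counts an AE whatever its cause. The UADE definition in 6.3 requires a link to the device and an effect not previously identified in nature, severity or degree of incidence, or another unanticipated serious problem associated with the device. An SAE rated as not related to the device need not qualify.
- Protocol 6.2.2 lists identified risks, including vomiting, constipation and weight decrease. A hospitalisation for one of these is serious under 6.3 but may not be unanticipated.
- SAP 9.1 also counts events that begin before the device is used: "If the start date of the event is before the first administration of RELiZORB, the event will be summarized under Standard of Care". An SAE in that window, in a subject with no earlier exposure, cannot be a device effect. This covers only about 14 days, and only subjects who later used the device, because the table is on the Safety population.

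**Step 3: effect on Table 14.3.1.2.** SAP 6.1 sets the percentage denominator as all subjects in the relevant population, here the Safety population, N. Let a be the subjects with a given term and s those whose only events under it are non-UADE SAEs (ignoring UADEs, which have their own tables).

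- Full incidence = a/N.
- Incidence shown = (a − s)/N.
- Shortfall = s/N.

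SAP 3.3 gives planned enrolment of 30 to 40, and protocol 4.1 gives about 35. Taking these as stand-ins for N:

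| s | N = 30 | N = 35 | N = 40 |
|---|---|---|---|
| 1 | 1/30 = 3.3 points | 1/35 = 2.9 points | 1/40 = 2.5 points |
| 2 | 2/30 = 6.7 points | 2/35 = 5.7 points | 2/40 = 5.0 points |

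As an illustration with assumed counts, take a = 6 at N = 35. Full incidence is 6/35 = 17.1%. The table would show 4/35 = 11.4% if s = 2, and 2/35 = 5.7% if s = 4. A subject who also had a non-serious event under the same term is still counted, so the table can understate a term but need not.

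**The case against.** The best defence is that 9.1 promises a separate summary of SAEs, not one by term. The overview line is a summary by treatment. SAP 9.1 also says that AEs leading to discontinuation of enteral feeding will be summarised and listed, and they too get only an overview line and a listing. On that reading, 9.1.2 means only that there is no further breakdown, and a few added words would mend it. This is a fair account of what the authors may have meant, but not of what 9.1.2 says. It also leaves the main effect in place: an overview count gives no incidence by term, and SAEs are still out of Table 14.3.1.2.

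A second defence is that protocol 6.3 calls a UADE analogous to an SAE, that protocol 7.2.1 counts UADEs regardless of causality, and that UADEs are tabulated by relationship. If sites recorded every serious event as a UADE, all would appear by term in Tables 14.3.2.1 to 14.3.2.3 and the gap would close. That caveat stands as a possibility. However, the formal definitions in 6.3 differ, and the SAP gives the two classes separate overview lines, sections and listings.

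Third, the table shells are not in the text available. A footnote there could state what Table 14.3.1.2 excludes, but it would not reconcile 9.1 with 9.1.2.

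Finally, presenting serious and other AEs separately is a legitimate layout, and with 30 to 40 subjects a full listing loses no event. That limits the harm. The layout works only if both parts are tabulated.

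**Conclusion.** The concern holds and should be fixed. The contradiction between 9.1 and 9.1.2 is explicit and depends on no assumption. So does the absence of any SAE table by term in SAP 12.1.

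The understatement in Table 14.3.1.2 is conditional. It arises only if some subject's sole event under a term is an SAE not classed as a UADE. The documents give no rate for this, and the number may be zero. The shortfalls above use planned enrolment in place of the Safety population, whose final size the documents do not give.

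The consequence is limited, since the overview count and Listing 16.2.6.5 remain and no efficacy result is affected. A reader wanting complete incidence by term would still have to rebuild it by hand. Separately, it is unclear whether the overview's line for all AEs includes SAEs and UADEs, because the exclusion sentence sits in the SOC/PT paragraph.

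**What to change.** Preferred: delete the exclusion sentence in SAP 9.1 and state that Table 14.3.1.2 includes every AE, serious or not, UADEs among them, with UADEs also shown in Tables 14.3.2.1 to 14.3.2.3.

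Minimum, if the exclusion is kept: add one SAE table by SOC, PT and treatment period, sourced from Listing 16.2.6.5.

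In either case, remove from 9.1.2 the words saying that SAEs are not summarised, and confirm that the overview's line for all AEs includes SAEs and UADEs.

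The cost is two or three sentences, or one extra table, from data already collected. Percentages in Table 14.3.1.2 may rise slightly under the preferred option, and a footnote is needed where an event appears in more than one table.
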